9. SAFETY ANALYSIS

Safety analyses will be performed on the safety population defined in Section 4.6. For each of the safety parameters, a summary statistic will be provided overall and by clinical diagnosis groups and no inferential testing will be performed.

9.1. Adverse Events

An AE is defined as any untoward medical occurrence or an already present event that worsens either in intensity or frequency. A DaTSCANTM-emergent AE, globally defined as treatmentemergent AE (TEAE), is defined as an AE that starts on or after the time of the injection of DaTSCANTM until the follow-up visit at 3 (\pm 1) days later regardless of its causal relationship to investigational agent, therefore it can be any unfavourable and unintended sign (including an abnormal laboratory finding), symptom, or disease temporally associated with the exposure to the IMP, whether or not considered related to that product. A serious adverse event (SAE) is defined as any event that results in death, is immediately life threatening, requires inpatient hospitalization or prolongation of existing hospitalization, results in persistent or significant disability/incapacity, is a congenital anomaly/birth defect, or is another important medical event defined in protocol Section 10.3.5.1. Other significant AEs are defined as laboratory abnormalities that qualify as AEs (other than those meeting the definition for serious) and any events that lead to an intervention (including premature discontinuation of IMP, dose reduction, or significant additional concomitant therapy).

AE terms recorded by the clinical site will be mapped to SOC and PT using MedDRA version 22.0 or later. If the start date, end date, severity, or relationship of AE is missing, it will be imputed as shown in Section 4.4.

The following summaries of AEs by SOC and PT will be provided:

- All AEs
- All TEAEs
- All SAEs
- All treatment-emergent SAEs
- All TEAEs resulting in study treatment discontinuation
- All related TEAEs
- All related treatment-emergent SAEs
- All other significant AEs
- All TEAEs by intensity
- All treatment-emergent SAEs by intensity
- All most common AEs (defined as AEs reported by at least 5% of the subjects).

If a subject experiences the same AE more than once with different intensity (mild, moderate, and severe), then the event with the highest intensity will be tabulated in "by intensity" tables. If a subject experiences multiple TEAEs under the same PT (or SOC), then the subject will be counted only once for that PT (or SOC).

In summary tables, AEs are sorted by alphabetical order of SOC, and then descending frequencies of PT.

Data listings will be provided for all AEs. The incidence of deaths and the primary cause of death will be displayed in a listing.

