9.1 Screening Visit

At the screening visit (within 28 days prior to the imaging visit), the following will be performed/recorded:

- Signed and dated informed consent
- Assign subject number
- Inclusion criteria and exclusion criteria (listed in Sections 7.2 and 7.3)
- Demographic information
- Medical and surgical history
- Neuropsychiatric history (including dementia history)
- Neurological examination
- Neuropsychiatric examination:
 - Mini-Mental State Examination
 - United Parkinson's Disease Rating Scale (UPDRS) Part III assessment
 - Hoehn and Yahr Scale for PD
 - WHIGET assessment for ET
- Vital signs (blood pressure, heart rate)
- Pregnancy test (serum β-hCG test; if applicable)
- Prior and concomitant medications
- Blood and urine samples for laboratory testing (see Table 2).
- AEs

The screening visit and baseline visit may be combined and conducted on the same day. All procedures for both visits have to be completed at this combined visit. Laboratory results for the subject must be available and assessed by investigators before the imaging visit is scheduled.

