9.4 Follow-up Visit (3 [±1] days after injection)

At the follow-up visit scheduled for 2 to 4 days after injection, the following will be performed/recorded (Table 1):

- Neurological examination
- Concomitant medications
- Clinical laboratory tests
- Physical examination
- Vital signs
- AEs

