10.3.5 Adverse events

All AEs/SAEs that occur after informed consent shall be recorded in the AE/SAE report form (see the Study Schedule of Events, Table 1).

Study personnel must remain vigilant for the occurrence of AEs after administration of IMP, particularly those that may be life threatening. Personnel who are trained in the acute management of anaphylaxis and other emergencies and who have access to appropriate clinical supplies must be immediately available for 1 hour after dosing. Treatment of SAEs should be primarily supportive of vital functions.

AE and DaTSCANTM-emergent AE definition: An AE is defined as any untoward medical occurrence or an already present event that worsens either in intensity or frequency. A DaTSCANTM-emergent AE is defined as an AE that starts on or after the time of the injection of DaTSCANTM until the follow-up visit at 3 (±1) days later. The DaTSCANTM-emergent AE does not necessarily have to have a causal relationship with exposure to the investigational agent. A DaTSCANTM-emergent AE can therefore be any unfavourable and unintended sign (including an abnormal laboratory finding), symptom, or disease temporally associated with the exposure to the IMP, whether or not considered related to that product.

The subjects will be closely observed and questioned for any kind of AE during the study procedures and throughout the study period with non-leading questioning (e.g., "How do you feel?"). The subjects will be instructed to immediately report any symptoms and signs to the study staff (i.e., between formal observations).

If an AE has already been reported it is not necessary to report each individual sign and symptom of that AE as a separate AE. For example, if myocardial infarction is reported as an AE, there is no need to report an elevated creatine phosphokinase, abnormal ECG, or other related signs, symptoms, or laboratory values as separate AEs.

All AEs/SAEs and all DaTSCANTM-emergent AEs/SAEs shall be collected up to the time point of finalisation of the last safety examination during the follow-up performed at 3 (± 1) days post-injection.

Causal relationship

Both the investigator(s) and Sponsor/contract research organisation (CRO) will perform a causality assessment on any AE, to assess whether or not there is a reasonable possibility (evidence to suggest) that the IMP caused the event.

The relationship of an AE with DaTSCANTM will be assessed and reported by the investigator as:

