2.2. Secondary Objectives

- To assess the striatal uptake of [¹²³I]ioflupane in healthy Chinese volunteers (no SDD).
- To assess safety parameters (haematology, biochemistry and urinalysis, and vital signs) and the adverse event (AE) profile in Chinese patients/HVs after a single IV administration of DaTSCANTM ioflupane (¹²³I) injection.

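### SAP 9.1 builds the 5% most-common-AE table and the other-significant-AE table on all AEs since consent, with no treatment-emergent version, so both also reflect the wait before injection

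*SAP*

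**What the plan says.** - **Start of recording.** Protocol 10.3.5: "All AEs/SAEs that occur after informed consent shall be recorded in the AE/SAE report form". Consent is taken at screening, and Protocol 9.1 times that visit: "At the screening visit (within 28 days prior to the imaging visit". No minimum gap is stated. Screening and baseline can share a day, but laboratory results must be assessed before imaging is scheduled.
- **End of recording.** Protocol 10.3.5 says AEs "shall be collected up to the time point of finalisation of the last safety examination during the follow-up". Protocol 9.4 places that visit: "At the follow-up visit scheduled for 2 to 4 days after injection".
- **Safety objective.** SAP 2.2 asks for the AE "profile in Chinese patients/HVs after a single IV administration", that is, what happens after dosing.
- **Tables.** SAP 9.1 defines a TEAE as an AE with onset from injection to follow-up. AEs and SAEs are each tabulated in an all-event and a treatment-emergent form. The related, by-intensity and discontinuation tables are treatment-emergent only. The two exceptions are the other-significant-AE table and the 5% table: "All most common AEs (defined as AEs reported by at least 5% of the subjects". Neither carries an onset limit or has a treatment-emergent counterpart. Protocol 12.6.1.6 also sets no onset limit for other significant AEs, and it does not mention a 5% table.

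**The concern.** Because SAP 9.1 uses AE and TEAE as distinct terms in one list, a programmer would apply these two bullets as written. An event that occurred only before injection could then count towards the 5% table. It could also count as other significant if it met that definition. For example, Protocol 10.3.3.3 sends subjects with protein or blood in the screening urine for infection work-up and treatment before study entry. If such a finding is recorded as an AE after consent, it may fall in the second table with no drug given.

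A list of events reaching 5% is a natural source for a short AE summary. As planned, which terms appear would depend partly on how long subjects waited between screening and imaging. That is visit scheduling and has nothing to do with the product.

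**Working it through.** **Inputs from the documents**
- Gap g from consent to injection: at most 28 days (Protocol 9.1).
- Follow-up f: nominally 3 days, range 2 to 4 (Protocol 9.4).
- Planned enrolment: 150 + 22 = 172 (SAP 3.1). The safety population is everyone injected (SAP 4.6).
- 5% line: 0.05 × 172 = 8.6, so at least 9 subjects. SAP 9.1 does not say whether 5% applies overall or within a diagnosis group; overall is assumed here.

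**Check against the plan's own figure.** The longest window is 28 + 2, 28 + 3 or 28 + 4 = 30, 31 or 32 days. This agrees with the roughly one month of participation in Protocol 6.3. The documents state no pre-injection share.

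**Pre-injection share = g / (g + f), with f = 3**

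| Gap (days) | Share |
|---|---|
| 1 | 1/4 = 25% |
| 7 | 7/10 = 70% |
| 14 | 14/17 = 82% |
| 28 | 28/31 = 90% |

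At 28 days the share is 28/30 = 93% with f = 2 and 28/32 = 87.5% with f = 4.

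**Effect on the 5% table (illustration).** Assume one preferred term with a constant background rate r per day, no drug effect, and the same gap for all 172 subjects.
- All-AE incidence = 1 − exp(−r(g + 3)).
- TEAE incidence = 1 − exp(−3r), whatever the gap.
- Chance of listing = P(X ≥ 9), with X binomial(172, incidence).

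The documents give no background rate, so a range is shown. Each cell gives incidence, then chance of listing.

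| r per day | TEAE basis | All AEs, g = 7 | All AEs, g = 14 | All AEs, g = 28 |
|---|---|---|---|---|
| 0.1% | 0.3%; <0.1% | 1.0%; 0.01% | 1.7%; 0.3% | 3.1%; 8% |
| 0.3% | 0.9%; <0.1% | 3.0%; 7% | 5.0%; 49% | 8.9%; 97% |
| 0.5% | 1.5%; 0.1% | 4.9%; 46% | 8.1%; 95% | 14.4%; >99% |

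The 0.5% row is high for a single term: over 30 days it means 1 − exp(−0.15) = 14% of subjects.

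**Does the drug still show?** Take a background risk of 5% per 30 days and a drug-caused risk of 5%, both assumed. With λ = −ln(0.95)/30, all-AE incidence is 1 − 0.95·exp(−λ(g + 3)). That gives 5.7% at a 1-day gap and 9.9% at 28 days. Without the drug effect the figures are 0.7% and 5.2%. The rate moves with both the drug and the gap.

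**The case against.** The strongest reply is that post-injection rates are already reported. SAP 9.1 plans all TEAEs by SOC and PT, sorted by descending frequency within SOC, so any TEAE at or above 5% can be found there. SAP 9 makes safety descriptive with no testing, and no document calls the 5% table the product's AE profile. This stands and limits the harm. It does not make the 5% table fit the post-dose objective, and no planned table isolates other significant events with post-injection onset.

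A reader might infer more than the documents support, in four ways:
- **That the rates do not reflect the drug at all.** Post-injection events are counted too; the gap dilutes and confounds the signal without replacing it.
- **That both tables count every AE since consent.** Other significant AEs are only laboratory abnormalities qualifying as AEs and events leading to an intervention. Scheduled blood and urine tests occur only at screening and follow-up (Protocol 10.3.3.2 and 10.3.3.3), so laboratory changes arising after screening would mostly be detected after injection. The probabilities above concern the 5% table only.
- **That 90% is typical.** It is the maximum; actual gaps are not given.
- **That PS-versus-HV differences would be biased.** The 7-day washout in Protocol 8.5 concerns users of traditional medicine for PD, whose number is unknown. All subjects share the 28-day limit and the wait for laboratory results. Unequal gaps are possible, but the documents do not show them.

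**Conclusion.** The point holds as a limited correction to the safety tables. Read literally, both tables admit events with onset before injection and have no treatment-emergent version, while the objective concerns events after administration. The pre-injection share of collection time is 70% at a 7-day gap and at most about 90% at 28 days with day-3 follow-up.

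The effect on the 5% table may be negligible or decisive, depending on an unstated background rate. At a 14-day gap with no drug effect, the chance of listing is about 0.3%, 49% or 95% at 0.1%, 0.3% or 0.5% per day, against about 0.1% or less on TEAEs. These figures assume a constant rate, a common gap and an overall 5% rule. The direction is the same throughout: longer gaps add background events. No efficacy result is touched, and the planned all-TEAE table preserves the post-injection incidence of each term.

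**What to change.** In SAP 9.1:
1. Reword the 5% bullet to *Most common TEAEs (reported by at least 5% of the subjects)*.
2. Add *Other significant TEAEs* beside the existing table of all other significant AEs.

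The second table should be added, not substituted. Protocol 12.6.1.6 sets no onset limit for other significant AEs, and SAP 11 declares no changes to the protocol's analyses. Replacing the table would depart from the protocol and would drop pre-injection events needing intervention from the significant-event summary. The 5% table is not specified in Protocol 12.6.1.6, so rewording it creates no such conflict.

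The cost is one reworded bullet and one extra table shell. TEAE status is already needed for other tables, and SAP 4.4 already has rules for missing onset dates. Pre-injection events stay in the all-AE table and the listings.

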
9.2. Clinical Laboratory Evaluations

Haematology, serum biochemistry, and urinalysis results will be summarized with descriptive statistics at each time point. Numeric haematology and serum biochemistry results will be summarized by actual result and change from baseline. Summaries by timepoint will include data from scheduled assessments only.

GE-001-024 Statistical A Version 1.0 Approved

n

GE Healthcare Ltd.

The occurrence of 1 or more changes from baseline, at each post-administration time point, greater than 40% and 80% of the span of the normal limits (not applicable to qualitative parameters), will be summarized by counts and percentages for haematology and serum biochemistry tests for the overall safety population and for each diagnostic group subset.

A shift table representing the shift from baseline category (High, Normal, and Low) to each postbaseline visit for haematology and serum biochemistry tests will be provided by counts and percentages for the overall safety population and for each diagnostic group subset.

All laboratory results will be displayed in separate data listings.

Statistical Analysis Plan. Protocol GE-001-024

9.3. Vital Sign

Vital sign measurements include systolic and diastolic blood pressure, and heart rate. Descriptive statistics of observations and changes from baseline in results for vital signs will be summarized by timepoint. Summaries by timepoint will include data from scheduled assessments only.

The occurrence of 1 or more changes from baseline, at each post-administration time point, greater than a pre-specified magnitude (20 mm Hg for systolic blood pressure, 10 mm Hg for diastolic blood pressure, 10 beats per minute for heart rate) will be summarized by counts and percentages for the overall safety population and for each diagnostic group subset.

Shifts from baseline during the treatment based on below, within, and above the normal ranges will be summarized by visit for the overall safety population and for each diagnostic group subset. Data from both scheduled and unscheduled assessments will be included for analysis of minimum and maximum post-baseline values in the shift table.

Vital Sign Parameter	Normal Range				
vitai Sign I arameter	Low	High			
Systolic BP (mmHg)	85	139			
Diastolic BP (mmHg)	60	89			
Heart Rate (beats/minute)	60	100			

Vital signs results at all time points will be displayed in a listing.

9.4. Physical Examination

Physical examination will include recording an assessment for the presence of abnormalities of the following: general appearance, lungs, cardiovascular system, and abdomen.

Descriptive statistics will be applied to summarize observed values at each time point. Shift table representing the shift from baseline status (Normal, Abnormal) to each post-administration time point will be prepared for the overall safety population and each diagnostic group subset.

Physical examination results will be displayed in a data listing.

9.5. Neurological Examination

Neurological examination will include recording an assessment for the presence of abnormalities of the following: level of consciousness, cranial nerves (II-XII), motor function, sensory function, proprioception/position sense of extremities, reflexes (biceps, triceps, patellar, ankle), mood and affect, cognitive function, cerebellar, speech, orientation, memory, and gait.

Descriptive statistics will be applied to summarize observed values at each time point. Shift table representing the shift from baseline status (Normal, Abnormal) to each post-administration time point will be prepared for the overall safety population and each diagnostic group subset.

Neurological examination results will be displayed in a data listing.

9.6. Injection Site Monitoring

Injection site findings will be summarized by time point for the overall safety population and each diagnostic group subset. Shift table representing the shift from baseline status (Normal, Abnormal) to each post-administration time point will be prepared as well for the overall safety population and each diagnostic group subset. All injection site monitoring results will be displayed in a data listing.

GE Healthcare Ltd.

10. INTERIM ANALYSES

No formal interim analysis is planned in this study.

GE Healthcare Ltd.

11. CHANGES TO THE PLANNED ANALYSIS

No changes to the statistical analyses section of the protocol are made in this SAP.

13. APPENDICES

13.1. Study Schedule of Events

		Treatment						
	Screening		Imaging Visit					
	Visit ^a	Baseline Visit ^a	Pre-injection			Post-injection		Follow-up
	Within 28 days prior to imaging visit	Within 28 days prior to imaging visit	Within 1 to 4 hours prior to injection	Within 30 min prior to injection	0	10 min	3 to 6 hours	3 (±1) days ^b
Informed consent	Х							
Subject number assignment	Х							
Demographic information	Х							
Inclusion/exclusion criteria	Х	Х	Х					
Medical and surgical history	Х							
Neuropsychiatric history (including dementia history)	Х							
Neurological examination	Х	Х						Х
Pregnancy test (if applicable)	Х		Х					
Prior and concomitant medication	Х							Х
Laboratory tests ^c	Х							Х
Physical examination		Х						Х
Neuropsychiatric examination ^d	Х	Х						
Clinical diagnosis		Х						
Vital signs (blood pressure, heart rate)	Х			Х			Х	Х
Thyroid blocking			Xe				Xe	
Injection site monitoring				Х	Х	Х	Х	
DaTSCAN [™] injection					Х			
SPECT imaging							Xf	
Adverse events	X							X

^a The screening visit and baseline visit may be combined and conducted on the same day.

^b Performed at 3 (±1) days after injection of DaTSCANTM

^c Some tests will only be performed at screening

^d Mini Mental State Examination, UPDRS-III, United Parkinson's Disease Rating Scale Part III; H&Y, Hoehn and Yahr and WHIGET assessment

^e The dosage and timing of administration will be based on investigator's discretion according to local practice of each site (e.g., to be administered within 1 to 4 hours prior to and 12 to 24 hours after injection of DaTSCANTM are just for reference)

^f Performed 3 to 6 hours after injection of DaTSCANTM

SIGNATURE PAGE

Date / Name

Signed By:

Date of signature: 21-Oct-2021 14:39:55 GMT+0000 Signed By:

Date of signature: 21-Oct-2021 14:54:45 GMT+0000

Justification / Role

Justification: Approved Role: Head of Biometrics

Justification: Approved Role: Head of Clinical Development
